3.2. Estimands

3.2.1. Estimand for Primary Efficacy Analysis (PFS)

Research Question: How does progression free survival time compare between subjects treated with unesbulin (PTC596) in combination with DTIC to those treated with DTIC alone (placebo + DTIC) in the population of subjects with unresectable or metastatic, relapsed or refractory LMS?

Subject Population: Subjects previously treated with 1 to 3 prior lines of systemic therapy, who are randomized to a treatment assignment (unesbulin+DTIC or placebo+DTIC) and further described in the protocol inclusion exclusion criteria.

Endpoint variable: Time from randomization to disease progression or Death due to any cause (whichever occurs first) with disease progression determined according to the RECIST 1.1 and assessed by ICR.

Population-level summary: The hazard ratio (HR) and 95% confidence interval (CI) between unesbulin and placebo

Treatment Condition: unesbulin+DTIC vs. placebo+DTIC

Intercurrent Event Strategy:

- a) Discontinuation of DTIC Treatment Policy
- b) Discontinuation of unesbulin While on treatment
- c) Start of subsequent anticancer treatment: While on treatment

3.2.2. Estimand for Overall Survival (OS)

Research Question: How does survival time compare between unesbulin treatment versus placebo in the population of subjects with unresectable or metastatic, relapsed or refractory LMS?

Subject Population: Subjects previously treated with 1 to 3 prior lines of systemic therapy, who are randomized to a treatment assignment (unesbulin+DTIC or placebo+DTIC) and further described the protocol inclusion exclusion criteria.

Endpoint variable: Time from randomization to death.

Population-level summary: The HR and 95% CI between unesbulin and placebo.

Treatment Condition: unesbulin+DTIC vs. placebo+DTIC

Intercurrent Event Strategy:

- a) Discontinuation of unesbulin Treatment Policy
- b) Discontinuation of DTIC Treatment Policy
- c) Start of subsequent anticancer treatment: Treatment Policy

3.2.3. Estimand for Objective Response Rate (ORR)

Research Question: How does tumor shrinkage (response) compare between unesbulin treatment versus placebo in the population of subjects with unresectable or metastatic, relapsed or refractory LMS as defined by the study's inclusion exclusion criteria?

Subject Population: Subjects previously treated with 1 to 3 prior lines of systemic therapy, who are randomized to a treatment assignment (unesbulin+DTIC or placebo+DTIC) and further described the protocol inclusion exclusion criteria.

Endpoint variable: Objective response (best overall response [BOR] of CR or PR) per RECIST 1.1 assessed by ICR.

Population-level summary: Proportion and Clopper Pearson 95% CI

Treatment Condition: unesbulin+DTIC vs. placebo+DTIC

Intercurrent Event Strategy:

- a) Discontinuation of unesbulin While on treatment
- b) Discontinuation of DTIC Treatment Policy
- c) Start of subsequent anticancer treatment While on treatment

3.2.4. Estimand for Duration of Response (DOR)

Research Question: What is the difference between subjects treated with unesbulin + DTIC to those treated with placebo+DTIC in the DOR, defined as time from first disease response to disease progression or death (whichever occurs first)?

Subject Population: Subjects previously treated with 1 to 3 prior lines of systemic therapy, who are randomized to a treatment assignment (unesbulin+DTIC or placebo+DTIC) and have tumor response.

Endpoint variable: Objective response per RECIST 1.1 assessed by ICR.

Population-level summary: Median and 95% CI

Treatment Condition: unesbulin+DTIC vs. placebo+DTIC

Intercurrent Event Strategy:

- a) Discontinuation of unesbulin While on treatment
- b) Discontinuation of DTIC Treatment Policy
- c) Start of subsequent anticancer treatment While on treatment
- d) Disease response (objective response rate [ORR]) Principal stratum

3.3. Multiplicity

A hierarchical (fixed sequence) testing procedure will be applied in the mITT analysis set. If the primary endpoint is significant at the 0.025 level (1-sided), then the key secondary endpoint (OS) will be tested in sequence. Additionally, tests for the secondary endpoints will be performed in sequence.

For the interim analysis of the primary endpoint (PFS), alpha allocation will be controlled for the key secondary endpoint OS as a separate group sequential design and monitoring will be performed at the interim and the final analysis timepoints by using the Lan-DeMets spending function that approximates the O'Brien-Fleming approach. The family-wise significance level is 0.025, with 0.000184 allocated at the interim analysis.

3.4. Missing Data

For the primary analysis of PFS only observed disease response data will be used. Data for subjects without progression or without any scans will be censored as described in Table 3.

3.5. Interim Analysis

One interim analysis of the study's primary endpoint (PFS) was planned to be performed when approximately 36% of the PFS events occur (approximately 88 events). An O'Brien-Fleming spending function will be used to calculate the sequential HR boundaries based on the actual number of PFS events.

Assuming there are 88 events at this interim analysis, then the study may stop for efficacy if the observed HR is less than 0.447 or stop for futility if the observed HR is more than 0.67.

Based on the results of planned interim analysis, the Data Monitoring Committee recommended discontinuing the study due to futility.

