In addition to Study PTC596-ONC-007-LMS, an initial Phase 1 study (PTC596-ONC-001-AST) in subjects with advanced solid tumors was completed, and 2 investigator-initiated Phase 1b studies, PTC596-ONC-004-OVA (subjects with newly diagnosed ovarian cancer) and PTC596-ONC-006-DPG (pediatric subjects with diffuse interstitial pontine glioma or high-grade glioma), are ongoing.

For similar reasons in the design of Study PTC596-ONC-007-LMS, PTC considers DTIC to be the most appropriate comparator for the intended population in Study PTC596-ONC-008-LMS. DTIC induces cytotoxicity by acting as an alkylating agent. It is a widely available generic drug that is often used as monotherapy or in combination with other therapies in advanced STS. DTIC as a monotherapy can achieve a PFS of 1.5 to 2.6 months (Hensley 2017, Blay 2019), and it is an acceptable choice to consider in the refractory setting for LMS because it is relatively well tolerated and given on a convenient schedule. Additionally, there is existing precedent for DTIC use as a single-agent comparator in the development of new treatments for LMS. During the clinical development of trabectedin for LMS, single-agent DTIC was used as the comparator arm during randomized Phase 2 and 3 studies (Demetri 2016, Patel 2019).

Additional information, including a description of unesbulin's chemistry, pharmacology, safety, and preliminary antitumor activity in models of LMS is provided in the current version of the Investigator's Brochure (IB).

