8.2. Sample Size Determination

The sample size for the primary analysis was computed based on the comparison of PFS between subjects randomized to unesbulin plus DTIC and subjects randomized to placebo plus DTIC. The median PFS was assumed to be approximately 1.5 to 2.5 months for the placebo plus DTIC group and more than 4 months for the unesbulin plus DTIC group. With an overall one-sided alpha level of 0.025, a total of 245 events are required to achieve at least 90% power at a hazard ratio of 0.5. Assuming 19 months of enrollment time, a minimum follow-up period of 6 months for the primary endpoint, and approximately 11.5% uniform dropout rate, a total of 300 subjects are planned to be randomized.

One interim analysis will be performed when approximately 36% of the PFS events occur (approximately 88 events). The study may stop for both efficacy and futility. The study may stop for efficacy if the observed hazard ratio is less than 0.447, and the study may stop for futility if the observed hazard ratio is more than 0.67.

The alpha allocation will be controlled separately at the interim and the final analysis timepoints by using the Lan-DeMets spending function that approximates the O'Brien-Fleming approach. The family-wise significance level is 0.025, with 0.000184 allocated at the interim analysis and 0.024816 at the final analysis.

For the key secondary endpoint OS, sample size is based on detecting a hazard ratio of 0.625 (median OS of 10 months versus 16 months, for placebo plus DTIC vs unesbulin plus DTIC, respectively) and a minimum 15-month follow-up. With 184 events (among 265 subjects) a 1-sided 0.025 level log-rank test will have approximately 84% power.

A separate group sequential design and monitoring will be performed for OS, with one interim analysis performed when at least 60% of the OS events occur and a final OS analysis when 184 events occur. The alpha allocation will be controlled by using the Lan-DeMets spending function that approximates the O'Brien-Fleming approach.

Data from the additional 45 subjects enrolled with at least 4 prior lines of therapy will not be included in the primary analysis; rather, the efficacy analysis of data from these subjects will be considered exploratory and included as a sensitivity analysis only.

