3.7. Changes to Protocol Specified Analysis

There are no changes in the protocol-specified analyses of efficacy (primary, secondary, and exploratory), safety, and PK endpoints. Exploratory analyses for the patient-reported outcomes and biomarkers will not be performed due to futility of the primary efficacy endpoint.

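### Is the futility cut of HR 0.67 at 88 PFS events too strict to count as futility?

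*SAP*

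**What the plan says.** Protocol section 8.2 sets the design: "a total of 245 events are required to achieve at least 90% power at a hazard ratio of 0.5", at one-sided alpha 0.025. The assumptions behind it are these: "The median PFS was assumed to be approximately 1.5 to 2.5 months for the placebo plus DTIC group and more than 4 months" on unesbulin plus DTIC. One interim is planned at about 88 events (36%), with an efficacy cut of HR 0.447. For futility, "the study may stop for futility if the observed hazard ratio is more than 0.67".

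SAP section 3.5 repeats both cuts on the assumption of 88 events (the trial may "stop for futility if the observed HR is more than 0.67") and names one method: "An O'Brien-Fleming spending function will be used to calculate the sequential HR boundaries based on the actual number of PFS events". It then records the outcome: "the Data Monitoring Committee recommended discontinuing the study due to futility". SAP section 3.7 says that the patient-reported outcome and biomarker analyses "will not be performed due to futility of the primary efficacy endpoint".

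Neither document gives a conditional-power, predictive-power or beta-spending criterion for 0.67. Protocol section 3.1 leaves the detailed conduct of the interim to the DMC Charter and the DMC SAP, which are not among the documents reviewed.

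**The concern.** Futility normally means that the trial is unlikely to succeed if it continues. At an interim HR of 0.67 that is not so here: most trials sitting at the cut would go on to win, and an HR between 0.67 and 0.767, called futile at the interim, would be a positive result at the end.

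The assumed medians also allow effects weaker than HR 0.5. Control at 2.5 months against just over 4 months gives an HR just under 0.625 with exponential PFS. The background in Protocol section 1.2 goes slightly higher for control ("DTIC as a monotherapy can achieve a PFS of 1.5 to 2.6 months").

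The one method named in SAP section 3.5 does not appear to produce 0.67. The trial was then stopped for futility, and the SAP uses that word to explain the dropped exploratory analyses. If the cut were wrong or contradicted the design, the plan would have given up a large part of its power without saying so, and readers could take the stop as evidence of no effect.

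**Working it through.** **Inputs.** 2:1 randomization (Protocol section 5.6), so information = events × 2/9. Interim 88 events, final 245, t = 88/245 = 0.359. Interim alpha 0.000184, final 0.024816 (Protocol section 8.2).

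**Reproducing the plan's figures.**
- Interim SE of log HR = 1/√(88 × 2/9) = 0.2261.
- Alpha 0.000184 gives z = 3.562, and exp(−3.562 × 0.2261) = 0.447. This matches the stated efficacy cut.
- Solving P(Z1 < 3.562, Z2 > c) = 0.024816 under the null, with futility non-binding, gives c = 1.961. The final HR threshold is exp(−1.961/√(245 × 2/9)) = 0.767.

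**Where 0.67 fits.**
- False stop at HR 0.5: ln(0.67/0.5)/0.2261 = 1.294, upper tail 9.8%.
- Cut for exactly a 10% false stop at HR 0.5: 0.5 × exp(1.2816 × 0.2261) = 0.668.
- An O'Brien-Fleming-type beta-spending cut (beta 0.10 at HR 0.5) would be about 0.88, so the spending function named in SAP section 3.5 does not give 0.67.

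**Conditional power at the cut.** Z1 = −ln(0.67)/0.2261 = 1.771.
- Current trend: Φ((1.771/√0.359 − 1.961)/√(1 − 0.359)) = Φ(1.24) = 89%.
- Flat-prior predictive power is 77%. If the true HR is 1.0, conditional power is 13%.
- Above the cut, trend conditional power falls: 80% at an interim HR of 0.70, 58% at 0.75, 35% at 0.80, 17% at 0.85.

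**Power with and without the stop.** Power with the stop = P(Z1 > 3.562) + P(1.771 < Z1 < 3.562, Z2 > 1.961), with means −ln(HR) × √(events × 2/9) and correlation √0.359.

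| True HR | P(futility stop) | Power, stop ignored | Power, stop always followed |
|---|---|---|---|
| 0.50 | 9.8% | 99.9% | 90.2% |
| 0.556 (2.5 vs 4.5 months) | 20.4% | 99.1% | 79.5% |
| 0.625 (2.5 vs 4.0 months) | 37.9% | 93.4% | 61.1% |

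The probability of stopping at a true HR of 1.0 is 96%. Trial simulations (300 subjects, 2:1, 19 months of uniform accrual, exponential PFS, no dropout, 4,000 runs per case) gave 61.0% to 62.4% with the stop at 2.5 vs 4.0 months, and 93.6% to 93.7% without it.

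**Range of effects in the assumed medians.** With unesbulin at 4 months, control at 1.5, 2.0 and 2.5 months gives HR 1.5/4 = 0.375, 2/4 = 0.5 and 2.5/4 = 0.625. The design HR is the middle of that range. The protocol puts the unesbulin median above 4 months, so 0.625 is a limit that the range does not reach.

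**Effect of loosening the cut.** A cut of 0.84 would hold power at 86.7% for HR 0.625 and 98.9% for HR 0.50. It would lower the probability of stopping at a true HR of 1.0 from 96% to 78%.

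**The case for a change.** The strongest case for a change is that the arithmetic is right and the documents are silent. A fixed design needs 99 events for 90% power at HR 0.5, and the plan calls for 245. The futility stop is what brings those 245 events down from 99.9% to about 90%, and nobody says so. At HR 0.556, inside the assumed range, power with the stop is already below 80%. The patient-reported analyses were to be descriptive only (Protocol section 8.4.8.2), so statistical futility is a weak reason to drop them.

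Part of this stands. Neither document states the basis of 0.67 or its behavior away from HR 0.5, and the O'Brien-Fleming sentence explains only the efficacy cut. The cut is an HR hurdle close to the design effect, and crossing it does not by itself show a low chance of success.

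The rest does not make the plan wrong. The protocol claims no power at 0.556 or 0.625. Wanting an early signal near the design effect before committing to 245 events is a legitimate choice in a Phase 2/3 trial, and neither document promises a conditional-power rule. The omitted exploratory analyses are disclosed in SAP section 3.7, and their absence alters no efficacy conclusion.

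**Conclusion.** No change is called for. Event count, design HR, stated power and futility cut agree with one another: about a 10% false stop and 90.2% power at HR 0.5. The 10% false-stop reading is an inference from the numbers. The stated 90% minimum would also hold with the stop ignored, but only with the stop in force is it a close match.

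The cost for weaker effects is real: 61% instead of 93% at HR 0.625. It rests on exponential PFS, a limiting pair of medians and a permissive stop being followed every time. A looser cut exchanges that loss for fewer early stops of an ineffective treatment (78% instead of 96%), which is a fair trade-off either way. It would also now have no effect, because the interim has been held and the DMC has made its recommendation.

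The missing rationale is a gap in documentation that the DMC Charter or DMC SAP may fill. SAP section 5.1.1 already provides for the PFS hazard ratio with its 95% CI, so readers of the study report can judge the effect from the estimate. The observed interim HR and event count are not in these documents, so nothing here bears on whether the DMC applied the rule correctly or whether the drug works.

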3.6. Data Definitions and Analysis Issues

3.6.1. Baseline Definition

The Randomization Visit will be defined as Day 1 of the study. For all endpoints, unless otherwise specified, the baseline value will be the latest pre-randomization assessment with a non-missing value, including those from unscheduled visits. If time is not collected, Day 1 assessments are assumed to be taken prior to first dose and used as baseline.

For the purposes of calculating summary statistics of the outcome measures, change from baseline will be derived as follows:

• Change from baseline = post-baseline value – baseline value

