randomized.

^b Specified time window is ± days. Unesbulin/placebo should not be dosed on consecutive days, and preferably at least 3 days (72 hours) between each unesbulin/placebo dose. The window for completion of the activities associated with Cycle 1 Day 1 and Cycle 2 Day 1 may be divided between a 2-day span. ^c Concomitant medications involve a complete medication reconciliation, including medications used for tolerability (eg, antiemetics and antidiarrheals). ^d Pathology review to confirm the histologic diagnosis of leiomyosarcoma is required. An outside pathology report documenting leiomyosarcoma is acceptable.

^e Full physical examination should be done at screening and EOT visits. Symptom-directed physical examination can be done at all other timepoints.

^f Assess weight on the day of DTIC administration; modify dose of DTIC if >10% change from baseline (or the last time the dose was changed).

⁹ Local laboratory testing is acceptable. Screening laboratory assessments and urinalysis must be collected within 3 weeks of Cycle 1 Day 1. Cycle 1 Day 1 laboratory assessments may be collected up to 24 hours before the first dose, but this window may be extended up to 72 hours for sites if it is impacted by laboratory working hours. For subsequent cycles, laboratory assessments may be collected up to 48 hours before dosing. On Day 1 Week 1 of each cycle, all laboratory assessments should be performed. On Day 1 of Weeks 2 and 3 of Cycles 1, 2, and 3, a CBC and CMP should be assessed for each subject. After Cycle 3, clinical laboratory assessments are required only once every cycle instead of on a weekly basis. If DTIC is held due to toxicity (see Section 3.3), then laboratory assessments should be completed while dosing with unesbulin/placebo continues. If DTIC is interrupted or held, then laboratory assessments should be done within 24 hours of resuming dosing with DTIC and continue on a weekly basis for the first 3 weeks after DTIC reintroduction. For subsequent cycles, the clinical laboratory assessments may be performed at a minimum of once per cycle or more frequently per the investigator's discretion to ensure that the subject meets the protocol-defined safety criteria in Section 3.3.

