Laboratory tests include: (1) CBC (hemoglobin, hematocrit, mean corpuscular volume, mean corpuscular hemoglobin, mean corpuscular hemoglobin concentration), WBC count, WBC differential (may be automated or manual as per institutional standards), RBC count, lymphocytes, monocytes, neutrophils, band neutrophils (if reported), eosinophils, basophils, platelets; and (2) CMP: albumin, alkaline phosphatase, total bilirubin, bicarbonate, blood urea nitrogen, calcium, chloride, creatinine, glucose, potassium, total protein, AST, ALT, and sodium.

^h For women of childbearing potential, a serum pregnancy test should be performed at screening (with a window of 7 days) and a urine pregnancy test should be performed within 24 hours of Day 1 of Cycle 1. A urine or serum pregnancy test should be performed within 24 hours prior to dosing on Day 1 of Cycle 2 and continuing every 2 cycles beginning at Cycle 4.

ⁱ For subjects not participating in the PK assessment, a single ECG should be collected on Day 1 of the first 3 treatment cycles only, approximately 2 hours after DTIC infusion. If DTIC is interrupted, then the single ECG should be collected approximately 2 hours after DTIC infusion and recorded on an unscheduled case report form page.

^j For subjects participating in the PK assessment, a single ECG should be taken as follows:

• Predose and 1.5, 4, and 8 hours postdose on Day 1 of Cycles 1 and 3 concurrent with intensive PK sampling for DTIC/AIC.

- Predose and 2, 4, 6, and 8 hours postdose on Day 2 of Cycles 1 and 3 concurrent with intensive PK sampling for unesbulin.
- Approximately 2 hours after DTIC infusion on Cycle 2.

^k Pretreatment, baseline imaging should be performed ≤14 days before Cycle 1 Day 1. On-treatment imaging should be performed every 6 weeks (±7 days). After Cycle 8, scans may be performed every 9 weeks. If any subject responds with a CR or PR at any assessment, then the subsequent confirmatory scan should be performed 4 weeks (+5 days) after the previous scan where the objective response was first evidenced. If the subject withdraws from the study for reasons other than progression of disease, EOT imaging should be performed if the last scan was ≥3 weeks earlier. Subjects should be followed with the same imaging procedure throughout the study. Computed tomography scans or magnetic resonance imaging may be used as clinically indicated.

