One treatment cycle will constitute 21 days. DTIC will be administered on Day 1 of each 3-week treatment cycle. Unesbulin or placebo tablets will be administered on Days 2 and 5 of Week 1 and Days 1 and 4 of Weeks 2 and 3 of each 3-week treatment cycle (Note: the preferable duration between 2 doses of unesbulin/placebo is approximately 72 hours). Based on the results from a food effect assessment in the ongoing Phase 1b Study PTC596-ONC-007-LMS, it is recommended that unesbulin/placebo be administered with food.

All subjects will receive treatment until evidence of disease progression, unacceptable toxicity, or other withdrawal criteria are met. No crossover will be permitted.

Subjects will undergo weekly assessments throughout the study. The schedule of all study efficacy, safety, PK, and laboratory assessments is shown in Table 1, including a window for completion of the activities associated with each visit. Of note, activities designed to be completed in a single day, for example, PK sampling from before dosing to 8 hours postdose, may not be split up between the 2 days of a window.

An end-of-treatment (EOT) assessment should be performed within 30 days after the end of treatment or until recovery from or stabilization of the AE, whichever occurs latest. For subjects requiring immediate initiation of a new treatment option, the EOT visit may be completed earlier. The EOT assessments are outlined in Table 1. A safety follow-up assessment should be performed by telephone call approximately 30 days (\pm 3 days) after the EOT to assess AEs and concomitant medications. Survival follow-up (sFUP) assessments should be performed by phone every 3 months (\pm 7 days) after the EOT until the later of 184 events or 2 years after the last subject is randomized.

PK Assessment

Approximately 12 randomized subjects will participate in a PK substudy at selected sites. These subjects will be assessed for PK of unesbulin, DTIC, and AIC. The target is for approximately 7 PK evaluable subjects in the unesbulin group to complete Cycle 3.

For the DTIC/AIC PK assessment, blood samples will be collected following an intensive schedule at predose and up to 24 hours postdose on Day 1 of Cycles 1 and 3. Sparse blood samples will be collected at predose and 1.25 and 4 hours postdose (start of infusion) on Day 1 of Cycles 2 and 4.

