6.5. Electrocardiogram (ECG)

ECG parameters (PR, RR, QRS, QT, QTcF, QTcB) and heart rate (HR) actual value and change from baseline will be summarized by treatment group and the overall population. Each subject's triplicate measurements will be averaged at a given time point before the summary. The number of non-missing values, mean, standard deviation, median, and range (minimum and maximum) will be presented. Change will be calculated as the post baseline measurement minus the baseline measurement. If either the baseline or postbaseline value is missing, the observation will not be included in the change from baseline summary.

In addition, a categorical analysis of QTc intervals will be performed for each time point.

The number and percentage of subjects in each QTc interval (<450 msec, 450-480 msec, 481-500 msec, >500 msec) will be summarized at baseline and each of the subsequent time points.

Categories of changes from baseline (\geq 30 msec and \geq 60 msec), maximum QTc intervals at all post dose time points, and maximum changes from baseline will be summarized by visit.

ECG results (PR, RR, QRS, QT, QTcF, QTcB, and classification of Normality, Abnormality with Clinical Significance, or Abnormality without Clinical Significance) will be presented in data listings.

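### SAP 3.6.1 takes an untimed Day 1 ECG as pre-dose baseline, although outside the PK group the only scheduled Cycle 1 Day 1 ECG is about 2 hours after DTIC

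*SAP*

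**What the plan says.** SAP 3.6.1 opens with "The Randomization Visit will be defined as Day 1 of the study". Unless a section says otherwise, "the baseline value will be the latest pre-randomization assessment with a non-missing value, including those from unscheduled visits". It then adds the rule for untimed data: "If time is not collected, Day 1 assessments are assumed to be taken prior to first dose and used as baseline". Neither the introduction to SAP 6 nor SAP 6.5 defines a separate baseline for safety or ECG.

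SAP 6.5 uses that baseline for change in ECG parameters, for the categories of QTc increase of at least 30 and at least 60 msec, and for maximum change.

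Protocol Table 1 sets the ECG times. Footnote i, for subjects outside the PK assessment, says "a single ECG should be collected on Day 1 of the first 3 treatment cycles only, approximately 2 hours after DTIC infusion". SAP Appendix 1 repeats that footnote. Footnote j gives the PK subjects "Predose and 1.5, 4, and 8 hours postdose on Day 1 of Cycles 1 and 3", so they do have a Day 1 tracing before DTIC. Protocol 3.1 sizes that group: "Approximately 12 randomized subjects will participate in a PK substudy at selected sites". Table 1 marks a screening ECG for everyone.

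DTIC is given on Day 1 of each cycle and unesbulin/placebo starts on Day 2 (Protocol 3.1). SAP 2.3 and 6.1 both count DTIC as study drug.

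**The concern.** For an untimed Cycle 1 Day 1 ECG, the SAP assumes the opposite of what its own appendix schedules. Followed literally, the rule discards a valid pre-treatment ECG from screening and puts in its place a tracing taken after the first dose of study drug. Any acute effect of DTIC or its premedication then becomes part of the reference value. The tracing is also no longer a post-treatment observation.

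The wording has a second weakness. The general rule is anchored on randomization, while the untimed-data rule speaks of first dose. Table 1 has no randomization visit, and the protocol does not say that randomization happens on Cycle 1 Day 1. If it happens earlier, assessments made on Cycle 1 Day 1 before dosing fall outside the baseline.

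What is at stake is the descriptive safety output: QTc change tables and, under the second timing, change from baseline in laboratory values, vital signs and weight. SAP 3.7 drops only the patient-reported outcome and biomarker analyses after the futility recommendation, so these safety tables are still planned.

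**Working it through.** **Reach of the ECG schedule.** The documents state no percentage, so there is no plan figure to reproduce. Inputs: 345 planned subjects (300 + 45, Protocol 3.2) and about 12 PK subjects (Protocol 3.1).

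- Share with only a post-DTIC Cycle 1 Day 1 ECG = (N − n) / N = (345 − 12) / 345 = 333 / 345 = 96.5%.
- If all 12 PK subjects are in the cohort with 1 to 3 prior lines: (300 − 12) / 300 = 96.0% of that cohort.
- With 10 to 15 PK subjects among 345: 97.1% to 95.7%.
- Actual enrollment is not given. Assuming 150 to 250 enrolled and 12 in the PK group: 138 / 150 = 92.0% to 238 / 250 = 95.2%.

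These are shares of subjects with that schedule.

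**When the rule takes effect.** The outcome depends on two facts that the documents do not give.

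1. *Randomization on Cycle 1 Day 1, ECG time not collected.* The Cycle 1 Day 1 ECG is an SAP Day 1 assessment and is assumed pre-dose. It displaces the screening ECG.
2. *Randomization on Cycle 1 Day 1, ECG time collected.* The untimed rule does not apply. Outside the PK group the latest pre-randomization ECG is normally the screening one, which is the right baseline.
3. *Randomization before Cycle 1 Day 1.* SAP Day 1 is then an earlier day, so the untimed rule as written does not reach the Cycle 1 Day 1 ECG. Pre-dose laboratory values, vital signs and weight taken after randomization are excluded, and older values stand in. For laboratory tests, footnote g says "Screening laboratory assessments and urinalysis must be collected within 3 weeks of Cycle 1 Day 1"; the screening window for the other assessments is Day −28 to −1.

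The ECG problem arises only in case 1, and the displaced laboratory, vital-sign and weight baseline is the problem in case 3. The same subject cannot be in both.

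**Effect in case 1.** Let S be the screening QTc, P = S + d the Cycle 1 Day 1 post-DTIC QTc, and X a later value.

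- Intended change: X − S.
- Reported change: X − P = (X − S) − d.

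The documents give no value for d. For illustration only:

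| Assumed d (msec) | Change from screening | Reported change | In the ≥60 category? |
|---|---|---|---|
| +10 | +60 | +50 | Wrongly left out |
| 0 | +60 | +60 | Correct |
| −10 | +50 | +60 | Wrongly included |

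The same arithmetic applies at 30 msec. For d > 0, the subjects misclassified at 60 msec are those whose change from screening is at least 60 but below 60 + d.

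**Lost observation.** Footnote i gives these subjects three on-treatment Day 1 ECGs, in Cycles 1 to 3. If the first becomes baseline, one of the three leaves the post-dose series, including the maximum post-dose QTc that SAP 6.5 asks for.

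**The case against.** The strongest reply is that the rule may never be used. The protocol schedules ECGs by the hour, which makes it plausible that clock time is recorded, and then the number of affected subjects could be zero. This stands: the documents do not show whether time is collected. A reader might infer from the 96.5% that nearly every subject has a wrong baseline, but it is only a ceiling on reach.

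A reader might also infer that the rule hides a QTc effect of unesbulin. The documents do not support that. Unesbulin/placebo starts on Day 2, so in both arms this ECG comes after DTIC but before the blinded drug. The Cycle 2 and Cycle 3 Day 1 ECGs are also about 2 hours after DTIC, so a post-DTIC baseline would be time-matched to them. What it absorbs is an acute DTIC or premedication shift present in both arms, and that shift could be positive, negative or nil. The between-arm contrast is therefore much less exposed than the within-arm change. The absolute QTc bands in SAP 6.5, including the band above 500 msec, use no change score.

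It is fair, too, that the SAP wording seems to treat the Randomization Visit and the first dosing day as one, which would make the exclusion of pre-dose Cycle 1 Day 1 data largely theoretical. No document confirms it. Nothing in the documents shows that laboratory values drift between screening and first dose.

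These replies limit the consequence. They do not justify a rule that contradicts the SAP's own schedule.

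**Conclusion.** The untimed-data rule in SAP 3.6.1 is wrong for the Cycle 1 Day 1 ECG of subjects outside the PK group. It rests on an assumption that Protocol Table 1 and SAP Appendix 1 contradict. The harm is conditional: ECG clock time must be uncollected and the Randomization Visit must coincide with Cycle 1 Day 1. Under those conditions, up to 333 of 345 planned subjects (96.5%) could have a post-DTIC baseline. Their QTc changes would be shifted by an amount of unknown size and sign, and one of three on-treatment Day 1 ECGs would be lost. Within-arm summaries bear most of this.

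If randomization comes first, the fault is a different one: pre-dose Cycle 1 Day 1 laboratory values, vital signs and weight are excluded from the safety baseline. The two faults are alternatives and should not be added together.

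The primary endpoint is untouched, and no change in a between-arm safety conclusion has been shown. The rule should still be corrected before the safety tables are produced, because it is specific, wrong as written and nearly free to mend.

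A separate wording error sits in SAP 6.5: "Each subject's triplicate measurements will be averaged at a given time point before the summary", whereas Table 1 collects single ECGs. It needs correcting but is not evidence for the baseline point.

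**What to change.** In SAP 3.6.1:

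- For safety endpoints, define baseline as the last non-missing value before the first dose of either study drug, DTIC or unesbulin/placebo.
- For subjects outside the PK group, treat an untimed scheduled Cycle 1 Day 1 ECG as post-dose and use the screening ECG as baseline, unless an ECG is documented as taken before dosing. The exception matters, because declaring every Cycle 1 Day 1 ECG post-dose would discard a tracing known to be pre-dose.
- Keep the pre-randomization baseline for efficacy endpoints.
- State whether ECG clock time is collected and how the Randomization Visit relates to Cycle 1 Day 1.

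In SAP 6.5, replace the averaging of triplicates with wording that fits the single ECGs collected.

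Under this rule the planned share of subjects whose scheduled post-DTIC ECG could be taken as baseline falls from 96.5% to 0%. Outside the PK group the baseline is the screening ECG or a later one documented as pre-dose; PK subjects use their Day 1 predose ECG. The cost is SAP wording and one derivation rule, with no new data.
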